#### Section 4: Risks and Benefits

30. Are there any of the following risks associated with the research? Please check all that apply.

Use of identifiable audio or video for data collection.  Physical Risk  
 Economic Risk  Psychological Risk  
 Legal Risk  Social Risk

- Use of private records including educational records or medical charts
- Collection of information that would be reportable to authorities or collection of information that might render the subject prosecutable under the law (e.g. child abuse, alcohol abuse, alcohol abuse by a pregnant woman, danger to self or others.)

31. If you checked any boxes above, describe the nature of each risk and how you've attempted to minimize it. These risks must be present in the consent form. Click here to enter text.
32. What direct and societal benefits do you expect the subject(s) you enroll to receive from this study? *If there is no direct benefit to the subjects, simply state that. There is no direct benefit to the subjects.*
33. Have you notified all areas (personnel and facilities) that need to be prepared to assist you in your research?
  - N/A
  - Yes – please list area and contact person's title.

**HIPAA authorizations or waivers may be appropriate if you are collecting Protected Health Information (PHI) from a hospital, medical center, doctor's office etc.**

34. Check PHI that you are collecting
 

 
 Names
 
 Email addresses
 
 Device identifiers
 
 Web universal resource
 
 Any unique identifying serial numbers
 
 Geographical subdivisions smaller than a State, including street address, city, county, precinct, zip code
 
 Elements of dates related to the individual, i.e. birthdate, admission date, discharge date, death.
 
 Health plan beneficiary numbers; account numbers; certificate/license numbers
 
 Vehicle identifiers and serial numbers, including license plate numbers
 
	
 
 Phone numbers; fax numbers,
 
 Medical Record numbers
 
 Full face photographic
 
 Social Security Numbers
 

---	--
35. Does your study require HIPAA authorization or Waivers?
  - N/A
  - Full Waiver <http://www.usd.edu/research/irb-general-forms>
  - Partial Waiver <http://www.usd.edu/research/irb-general-forms>
  - Authorization Addendum (A study-specific Research Subject HIPAA Authorization (stand-alone) form must be attached)

**Select how your initial submission was made:**

---

Cayuse

Paper form or A-Tune

## Legacy Data: Amendment Form

\*required

### 1. What are you revising?

---

Consent Form

Advertisements

Questionnaire/Survey

Adding a site or location

Investigator Brochure

Letter(s) of permission

IRB approvals other than USD IRB

Administrative letter

Closed to accrual

Other

### 2. Change of Personnel:

---

Add Personnel

Remove Personnel

\*required

### 3. Is the change significant?

---

Yes

No

\*required

4. **Please describe the change.**

---

I made separate informed consent form both control and experimental group.

\*required

5. **What is the reason for the change?**

---

For more effective intervention

\*required

6. **How would the proposed revision change the level of risk to the subjects?**

---

Increase

Decrease

No change

\*required

7. **Will this have an impact on the study and/or participants?**

---

Yes

No

\*required

**8. Are there changes needed to the consent form?**

---

Yes

*Attach a copy of the revised consent with the changes tracked or underlined and a clean copy for the IRB date-stamp at the bottom.*

---

Do you have subjects enrolled with the previous consent?

---

Yes

No

No

**9. Attach all modified/updated documents:**

---

Informed Consent

Telephone scripts

Protocols from sponsors

Investigator brochure

Advertisements, flyers, posters

Surveys, questionnaires, interview questions

updated and original IRB application

CITI certificates

Final-0527-2021-Experimental Group Informed consent form.doc

[name]\_Consent\_Control Group by [name]-052621-Submit to JS.doc

\*required

**Select how your initial submission was made:**

---

Cayuse

Paper form or A-Tune

## Legacy Data: Amendment Form

\*required

### 1. What are you revising?

---

- Consent Form
- Advertisements
- Questionnaire/Survey

Adding a site or location

Investigator Brochure

Letter(s) of permission

IRB approvals other than USD IRB

Administrative letter

Closed to accrual

Other

### 2. Change of Personnel:

---

Add Personnel

Remove Personnel

\*required

### 3. Is the change significant?

---

Yes

No

\*required

**Please describe the change.**

---

4. 

- There were minor grammatical changes made to the consent statements and pre-test. There were also changes to the participant payment information and include both informed consent forms and the updated flyers. Additionally, we changed our post-test based on our usability test and community advisory board members' suggestions and added sections VIII and IX and have a safety plan listed in the consent statements. We added an additional language as follows "If you may find some of the questions to be sensitive in nature or experience emotional discomfort, you can reach out to a licensed counselor at the Helpline Center ([[name]]([contact]))". This information will be included in the informed consent form.

\*required

**What is the reason for the change?**

---

5. 

- Based on input and suggestions from our usability test and community advisory board members, we included additional questions that have been associated with cancer care and health behaviors.

\*required

**6. How would the proposed revision change the level of risk to the subjects?**

---

Increase

Decrease

No change

\*required

**7. Will this have an impact on the study and/or participants?**

---

Yes

No

\*required

**8. Are there changes needed to the consent form?**

---

Yes

*Attach a copy of the revised consent with the changes tracked or underlined and a clean copy for the IRB date-stamp at the bottom.*

---

Do you have subjects enrolled with the previous consent?

---

Yes

No

No

**9. Attach all modified/updated documents:**

---

Informed Consent

Telephone scripts

Protocols from sponsors

Investigator brochure

- ✓ Advertisements, flyers, posters
- ✓ Surveys, questionnaires, interview questions

updated and original IRB application

CITI certificates

2021---wMammogram flyer-submit -100121 for stamp .doc

Control Group Informed Consent Form-Clean version for stamp-100121.doc

Control Group Informed Consent Form-track change version-100121.doc

Control-Brochure-FINAL-9-30-21.pdf

Experiment GP-Informed Consent Form-Clean version for stamp-100121.doc

Experiment GP-Informed Consent Form-Track change version-100121.doc

Post-test Control Group-100121.doc

post-test-mobile web app -Experiment GP-100121.doc

Pre-test-all participants-100121.doc

USD IRB Amendment Application-100121.docx

\*required

**Select how your initial submission was made:**

---

Cayuse

Paper form or A-Tune

## Legacy Data: Amendment Form

\*required

### 1. What are you revising?

---

Consent Form

Advertisements

Questionnaire/Survey

Adding a site or location

Investigator Brochure

Letter(s) of permission

IRB approvals other than USD IRB

Administrative letter

Closed to accrual

Other

### 2. Change of Personnel:

---

Add Personnel

Remove Personnel

\*required

### 3. Is the change significant?

---

Yes

No

\*required

**4. Please describe the change.**

---

We have 2 days of focus group meetings instead of one day meeting.

\*required

**5. What is the reason for the change?**

---

Prospective focus group members request more time slots for their attendance.

\*required

**6. How would the proposed revision change the level of risk to the subjects?**

---

Increase

Decrease

No change

\*required

**7. Will this have an impact on the study and/or participants?**

---

Yes

No

\*required

**8. Are there changes needed to the consent form?**

---

Yes

No

**Attach all modified/updated documents:**

9. \_\_\_\_\_

Include the track changes version and a clean version in word format.

Informed Consent

Telephone scripts

Protocols from sponsors

Investigator brochure

Advertisements, flyers, posters

Surveys, questionnaires, interview questions

updated and original IRB application

CITI certificates

[Final-Follow-up focus group flyer-042722-request to Announcer.doc](#)

[Final-Follow-up focus group flyer-042722-request to Announcer.pdf](#)

**Attach other approved documents associated with this modification.**

---

10.

*(Only attach current approved versions)*

\*required

**Select how your initial submission was made:**

---

Cayuse

Paper form or A-Tune

## Legacy Data: Amendment Form

\*required

### 1. What are you revising?

---

Consent Form

Advertisements

Questionnaire/Survey

Adding a site or location

Investigator Brochure

Letter(s) of permission

IRB approvals other than USD IRB

Administrative letter

Closed to accrual

Other

### 2. Change of Personnel:

---

Add Personnel

Remove Personnel

\*required

### 3. Is the change significant?

---

Yes

No

\*required

4. **Please describe the change.**

---

I made separate informed consent form both control and experimental group.

\*required

5. **What is the reason for the change?**

---

For more effective intervention

\*required

6. **How would the proposed revision change the level of risk to the subjects?**

---

Increase

Decrease

No change

\*required

7. **Will this have an impact on the study and/or participants?**

---

Yes

No

\*required

**8. Are there changes needed to the consent form?**

---

Yes

*Attach a copy of the revised consent with the changes tracked or underlined and a clean copy for the IRB date-stamp at the bottom.*

---

Do you have subjects enrolled with the previous consent?

---

Yes

No

No

**9. Attach all modified/updated documents:**

---

Informed Consent

Telephone scripts

Protocols from sponsors

Investigator brochure

Advertisements, flyers, posters

Surveys, questionnaires, interview questions

updated and original IRB application

CITI certificates

Final-0527-2021-Experimental Group Informed consent form.doc

[name]\_Consent\_Control Group by [name]-052621-Submit to JS.doc

\*required

**Select how your initial submission was made:**

---

Cayuse

Paper form or A-Tune

## Legacy Data: Amendment Form

\*required

### 1. What are you revising?

---

- Consent Form
- Advertisements
- Questionnaire/Survey

Adding a site or location

Investigator Brochure

Letter(s) of permission

IRB approvals other than USD IRB

Administrative letter

Closed to accrual

Other

### 2. Change of Personnel:

---

Add Personnel

Remove Personnel

\*required

### 3. Is the change significant?

---

Yes

No

\*required

**Please describe the change.**

---

4. 

- There were minor grammatical changes made to the consent statements and pre-test. There were also changes to the participant payment information and include both informed consent forms and the updated flyers. Additionally, we changed our post-test based on our usability test and community advisory board members' suggestions and added sections VIII and IX and have a safety plan listed in the consent statements. We added an additional language as follows "If you may find some of the questions to be sensitive in nature or experience emotional discomfort, you can reach out to a licensed counselor at the Helpline Center ([[name]]([contact]))". This information will be included in the informed consent form.

\*required

**What is the reason for the change?**

---

5. 

- Based on input and suggestions from our usability test and community advisory board members, we included additional questions that have been associated with cancer care and health behaviors.

\*required

**6. How would the proposed revision change the level of risk to the subjects?**

---

Increase

Decrease

No change

\*required

**7. Will this have an impact on the study and/or participants?**

---

Yes

No

\*required

**8. Are there changes needed to the consent form?**

---

Yes

*Attach a copy of the revised consent with the changes tracked or underlined and a clean copy for the IRB date-stamp at the bottom.*

---

Do you have subjects enrolled with the previous consent?

---

Yes

No

No

**9. Attach all modified/updated documents:**

---

Informed Consent

Telephone scripts

Protocols from sponsors

Investigator brochure

- ✓ Advertisements, flyers, posters
- ✓ Surveys, questionnaires, interview questions

updated and original IRB application

CITI certificates

2021---wMammogram flyer-submit -100121 for stamp .doc

Control Group Informed Consent Form-Clean version for stamp-100121.doc

Control Group Informed Consent Form-track change version-100121.doc

Control-Brochure-FINAL-9-30-21.pdf

Experiment GP-Informed Consent Form-Clean version for stamp-100121.doc

Experiment GP-Informed Consent Form-Track change version-100121.doc

Post-test Control Group-100121.doc

post-test-mobile web app -Experiment GP-100121.doc

Pre-test-all participants-100121.doc

USD IRB Amendment Application-100121.docx

\*required

**Select how your initial submission was made:**

---

Cayuse

Paper form or A-Tune

## Legacy Data: Amendment Form

\*required

### 1. What are you revising?

---

Consent Form

Advertisements

Questionnaire/Survey

Adding a site or location

Investigator Brochure

Letter(s) of permission

IRB approvals other than USD IRB

Administrative letter

Closed to accrual

Other

### 2. Change of Personnel:

---

Add Personnel

Remove Personnel

\*required

### 3. Is the change significant?

---

Yes

No

\*required

4. **Please describe the change.**

---

We have 2 days of focus group meetings instead of one day meeting.

\*required

5. **What is the reason for the change?**

---

Prospective focus group members request more time slots for their attendance.

\*required

6. **How would the proposed revision change the level of risk to the subjects?**

---

Increase

Decrease

No change

\*required

7. **Will this have an impact on the study and/or participants?**

---

Yes

No

\*required

**8. Are there changes needed to the consent form?**

---

Yes

No

**Attach all modified/updated documents:**

9. \_\_\_\_\_

Include the track changes version and a clean version in word format.

Informed Consent

Telephone scripts

Protocols from sponsors

Investigator brochure

Advertisements, flyers, posters

Surveys, questionnaires, interview questions

updated and original IRB application

CITI certificates

[Final-Follow-up focus group flyer-042722-request to Announcer.doc](#)

[Final-Follow-up focus group flyer-042722-request to Announcer.pdf](#)

**Attach other approved documents associated with this modification.**

---

10.

*(Only attach current approved versions)*

\*required

IRB CODE NUMBER: 2019.053
NCT number: 05530603

University of South Dakota

Department of Social Work

**Intervention To Promote Breast Cancer Screening Among
American Indian Women**

Statistical Analysis

Date of Document: 09/24/2019

Statistical Analysis: Prior to our hypotheses tests, group equivalence in terms of baseline characteristics will be examined using t-tests and chi-square tests. For Hypothesis 1, investigators will compare the percentage of women from each condition who receive mammograms or have scheduled a mammography appointment using a chi-square test. Investigators will supplement this with logistic regression analyses to adjust for confounding covariates. For Hypothesis 2, the averages of score change (pre- to post-test) from the two conditions will be compared using the two-sample t-test, and/or the Wilcoxon rank-sum tests after assessing normality of the scores. The group difference in terms of changes in the given constructs will be tested by a mixed-effect analysis of variance (ANOVA). The mixed-effect ANOVA includes both within-subject (i.e., time: repeated measures) and between-subject factors (i.e., group: intervention versus control) and aims to examine whether there is an interaction between these two factors on the dependent variable. Bonferroni correction will be used to reduce the probability of Type 1 error for multiple comparisons. Investigators will supplement this with a regression analysis of score change in order to adjust for confounding covariates. For Hypothesis 3, averages of general satisfaction and effectiveness scores from each group will be compared using the two-sample t-test. Also, the percentage of participants from each group who endorse "yes" for the intention and recommendation items will be compared using the chi-square test. To minimize a potential non-participation bias, investigators will closely monitor and compare the first and fourth quartiles of responses for differences in background variables and key constructs. Investigators will also carefully document the response rate over the course of this project. IBM SPSS version 25 will be used for data analyses.

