6. From the beginning, being the initial contact of participant(s) through last contact with participant(s) please describe the task(s) they will be expected to perform. (How will you contact them? What will you have them do?) The proposed study addresses two specific aims with a multi-method, two-phase research project that will take place in South Dakota over a three-year period. The two phases are: (1) developing the wMammogram intervention (Aim 1) and (2) evaluating the feasibility and efficacy of the wMammogram (Aim 2). Phase 1 incorporates a Community Based Participatory Research (CBPR) approach and a series of focus groups with various stakeholders in AI communities to design a culturally informed and practically refined intervention. Phase 2 uses a randomized clinical trial (RCT) design with AI women. In phase one, after the approval of the Yankton Tribal Institutional Review Board (IRB), [name] will convene two focus groups ( $N=20$ ;  $n=10$  for each group). Each group will consist of AI community leaders/members and local health professionals with backgrounds in cancer and health management. The purpose of the two focus groups will be to obtain firsthand information about the general public/health care professionals' beliefs, attitudes, and values about breast cancer and screening, as well as barriers, motivators, and possible triggers for screening. In phase two, the wMammogram intervention will be implemented with AI women using the blinded RCT over a seven-day period. Assessments with a mixed methods approach will be conducted at three intervals: baseline, one-week post-intervention, six-month follow-up survey, and post-intervention focus group.
7. Have you attached letters of approval from any schools or businesses involved?
 

Yes       N/A

Section 2: Participants

8. Please state the maximum number of participants you plan on enrolling. **107**
9. Please describe the study populations by checking all that apply.
 

 Males	 Females	 University Students
 Non-English Speaking	 Students in Grades K-12	
10. Are you **specifically** targeting an ethnic group? Check any that apply.
 

 American Indian	 African American	 Caucasian

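### The Hypothesis 2 analysis does not ensure adjustment for each construct's own pre-test score; an ANCOVA would use data already collected and is nearly always more precise than the planned change-score comparison

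*SAP*

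**What the plan says.** The whole covariate plan is in the single Statistical Analysis paragraph of the SAP.

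- **Baseline.** "Prior to our hypotheses tests, group equivalence in terms of baseline characteristics will be examined using t-tests and chi-square tests". No list of variables and no threshold is given, and nothing says what follows from the result.
- **Hypothesis 1.** The main comparison is unadjusted: "investigators will compare the percentage of women from each condition who receive mammograms or have scheduled a mammography appointment using a chi-square test". Then: "Investigators will supplement this with logistic regression analyses to adjust for confounding covariates".
- **Hypothesis 2.** The main comparison is again unadjusted: "the averages of score change (pre- to post-test) from the two conditions will be compared using the two-sample t-test", with a Wilcoxon test and/or alternative, and a mixed-effect ANOVA that examines the time-by-group interaction. Then: "Investigators will supplement this with a regression analysis of score change in order to adjust for confounding covariates".
- **Multiplicity.** "Bonferroni correction will be used to reduce the probability of Type 1 error for multiple comparisons". The number of constructs is not given.

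No covariate is named for either regression. The Protocol describes Phase 2 as a randomised trial (question 6) and gives a maximum enrolment of 107 (question 8). Neither document gives a power calculation, effect size, standard deviation or pre-post correlation.

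**The concern.** In a randomised trial, baseline differences between the groups arise by chance. A covariate is useful to the extent that it predicts the outcome. Calling the adjustment variables confounders points the analyst towards imbalance instead, and leaves open which variables are used.

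This matters most for Hypothesis 2. The pre-test score of the same construct is normally the best available predictor of the post-test score. A change score uses it, but with its coefficient fixed at 1. That is efficient only when pre- and post-test are very highly correlated. At lower correlation, subtracting the pre-test score adds noise, and below a correlation of 0.5 the change score is less precise than the post-test score alone. The mixed ANOVA does not escape this: with two time points, its interaction test is the change-score t-test in another form.

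The regression of score change could repair this, but only if the pre-test score is in it. The SAP does not say that it is, and gives that model a supplementary role. At stake is precision in a small trial, together with an adjusted model whose content is settled only at analysis.

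**Working it through.** **Inputs.** From the Protocol: a maximum of 107 participants (question 8) and two Phase 1 focus groups totalling 20 (question 6). If those 20 count towards the maximum, the randomised part has 107 − 20 = 87. Assumed, because the documents give none of them: 1:1 allocation, two-sided alpha 0.05, a difference of 0.5 SD in the post-test score, equal pre- and post-test SD, no dropout, and pre-post correlation ρ from 0.3 to 0.8. The 107 itself cannot be reproduced, as no power calculation is stated.

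**Step 1: residual SD, in units of the post-test SD.**

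- Post-test score alone: 1
- Change score: √(2(1 − ρ))
- ANCOVA on the pre-test score: √(1 − ρ²)

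The ratio of ANCOVA variance to change-score variance is (1 − ρ²) / (2(1 − ρ)) = (1 + ρ)/2. This is below 1 for every ρ below 1: 0.65, 0.75, 0.85 and 0.90 at ρ = 0.3, 0.5, 0.7 and 0.8. Apart from one degree of freedom, ANCOVA is therefore never less precise.

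**Step 2: power.** Normal approximation: power = Φ(0.5 / (SD × √(4/N)) − 1.96). For example, with N = 107 and ρ = 0.5, √(4/107) = 0.193. The change score gives 0.5/(1 × 0.193) = 2.586, so Φ(0.626) = 73.4%. ANCOVA gives 0.5/(0.866 × 0.193) = 2.986, so Φ(1.026) = 84.8%.

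| ρ | N = 107: change | N = 107: ANCOVA | N = 87: change | N = 87: ANCOVA |
|---|---|---|---|---|
| 0.3 | 58.9% | 77.4% | 50.4% | 68.6% |
| 0.5 | 73.4% | 84.8% | 64.5% | 76.8% |
| 0.7 | 91.6% | 95.2% | 85.3% | 90.4% |
| 0.8 | 98.3% | 99.1% | 95.8% | 97.3% |

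The post-test score alone gives 73.4% (N = 107) or 64.5% (N = 87) throughout. No Bonferroni division is applied; it would lower both methods and leave their order unchanged.

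**Step 3: Hypothesis 1.** Logistic simulation, 5,000 runs per cell, assumed rates of 20% v 45%, one covariate. Power without and with adjustment:

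| Covariate log-odds per SD | N = 107 | N = 87 |
|---|---|---|
| 0.5 | 78.8% → 80.9% | 70.5% → 72.6% |
| 1.0 | 78.0% → 84.7% | 70.5% → 78.6% |
| 1.5 | 78.2% → 89.3% | 70.6% → 83.1% |

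The gain runs from about 2 to about 13 points. Nothing in the documents says how strongly age predicts screening uptake, so the low end is quite possible. Simulation error is about 0.6 points on each power figure.

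**Step 4: what a test-driven choice would do, if it were the rule.** Continuous outcome, difference 0.5 SD, N = 107, one covariate, 6,000 runs. Power unadjusted / adjusted only if baseline p < 0.05 / always adjusted:

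- R² 0.25: 73.2 / 74.2 / 84.0%. Share of the gain kept: (74.2 − 73.2)/(84.0 − 73.2) = 9%.
- R² 0.50: 72.9 / 74.8 / 94.7%. Share kept: (74.8 − 72.9)/(94.7 − 72.9) = 9%.

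Type I error under that rule was 3.4% to 4.2% across the cells with R² of 0.25 or 0.50 and N of 87 or 107.

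**The case against.** **The main tests are valid as they stand.** Under randomisation the change-score comparison is unbiased, and it already uses the pre-test score. This stands: the point concerns precision, not bias, and at ρ = 0.8 the gain at N = 107 is under one percentage point.

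**The supplementary regression may already include the pre-test score.** It may; the wording allows it. But the wording does not require it, and the model is only a supplement to the unadjusted tests.

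**A reader might infer that the baseline tests select the covariates,** because they come first and because confounding in a randomised comparison suggests chance imbalance. The SAP never says so and gives no threshold. The word is often used loosely for prognostic variables, and loss to follow-up can also unbalance the analysed groups. Step 4 therefore describes a hypothetical rule. Even under it, what is lost is most of the power gain from adjustment, not most of the power.

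**A reader might also infer an inflated false-positive rate.** The simulated rates are below 5%, so selection would be conservative.

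**A reader might infer that post-test items will be used as covariates,** since an amendment form in the Protocol records a changed post-test with "added sections VIII and IX". Nothing says these items are meant for adjustment, and the pre-test is not among the documents, so it may already contain them. A sentence restricting covariates to screening and pre-test data is a safeguard, not the correction of a stated error.

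**Replacing the baseline significance tests with a descriptive table** changes no hypothesis test. It is a reporting preference, and the point does not rest on it.

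**Conclusion.** The point holds for Hypothesis 2, as a low-cost gain in precision. The plan relies on unadjusted change scores and a time-by-group ANOVA and does not guarantee that the pre-test score enters the one adjusted model. At N = 107, ANCOVA would add about 19 points of power at ρ = 0.3 (77.4 − 58.9 = 18.5), 11 at ρ = 0.5 (84.8 − 73.4 = 11.4), 4 at ρ = 0.7 (95.2 − 91.6 = 3.6) and 1 at ρ = 0.8 (99.1 − 98.3 = 0.8). These sizes rest on the assumed effect, allocation, alpha, correlation and absence of dropout. The direction does not depend on the particular correlation.

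For Hypothesis 1 the benefit of a fixed covariate is real in principle, but its size depends on prognostic strength that the documents do not state, and it may be only about 2 points. The chi-square comparison would remain unadjusted and keep its present power.

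**What to change.** Amend the SAP as follows.

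1. **Hypothesis 2.** State that the regression always includes group, the same construct's pre-test score and age, whatever the baseline comparison shows, and that the group-difference estimate comes from this model. With the pre-test score included, regressing score change or the post-test score gives the same group coefficient, so the outcome can stay as written. Keep the t-test, Wilcoxon test and mixed ANOVA as supporting analyses.
2. **Hypothesis 1.** Replace the reference to confounding covariates with age, which is asked at screening (Protocol, questions 12 and 18). Add time since last mammogram only if it is actually recorded: the eligibility criteria show cut-offs, not a recorded interval, and the interval is undefined for women never screened.
3. **Source of covariates.** State that covariates come only from screening or the pre-test. Any covariate added after the data are seen belongs in a labelled sensitivity analysis.

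The cost is SAP wording and, for the pre-test score, one degree of freedom. No new data are needed for that score, because the planned change score already requires it. The sponsor should confirm that age is stored as a value and not only checked against the eligibility range.

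### Hypothesis 2 is tested on raw pre-to-post change; making ANCOVA on the pre-test score the deciding analysis would usually gain power at almost no cost

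*SAP*

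**What the plan says.** The SAP's Statistical Analysis paragraph gives four analyses for Hypothesis 2:

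- a comparison of mean change: "the averages of score change (pre- to post-test) from the two conditions will be compared using the two-sample t-test";
- a rank-based comparison of change (Wilcoxon), in addition or instead, depending on a check of normality;
- a mixed-effect ANOVA, read through its group-by-time interaction;
- a regression: "Investigators will supplement this with a regression analysis of score change in order to adjust for confounding covariates".

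Only the regression is ranked, as a supplement, and its covariates are not named. On multiplicity the SAP adds that "Bonferroni correction will be used to reduce the probability of Type 1 error for multiple comparisons", without saying how many comparisons there are.

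The Protocol (Section 1, item 6) states that "Phase 2 uses a randomized clinical trial (RCT) design with AI women" and that "Assessments with a mixed methods approach will be conducted at three intervals: baseline, one-week post-intervention, six-month follow-up survey". Section 2, item 8 caps enrolment at 107. The list of attachments in the amendment form (item 9) includes a pre-test for all participants and a post-test for each arm.

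**The concern.** The change score subtracts the whole pre-test score, which amounts to fixing the slope of post-test on pre-test at 1. Unless the true slope is near 1, that leaves avoidable noise in the comparison. ANCOVA estimates the slope instead.

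The ANOVA does not help. With two waves its interaction F is the square of the change-score t, so it is the same test. With the six-month wave added the two tests differ, but the ANOVA still has no baseline covariate.

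The pre-test score is already collected and enrolment is capped, so extra precision has to come from the analysis. The promised Bonferroni correction makes each test stricter, which leaves less power to spare.

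**Working it through.** **Inputs from the documents.** Randomised intervention versus control; pre-test and post-test scores; at most 107 women; a Bonferroni correction with no stated divisor. There is no power calculation for Hypothesis 2 to reproduce.

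**Assumptions.** Two-sided 5%; 1:1 arms (53 v 54); true difference of 0.5 post-test SD; r = 0.3, 0.5, 0.7; k = post-test SD / pre-test SD, with k = 1 unless stated; Bonferroni divisor m = 1, 3 or 5; normal scores.

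**Variances, with pre-test SD = 1.**

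- Change score: 1 + k² - 2rk
- ANCOVA residual: k²(1 - r²)
- Difference: (1 - rk)², which is never negative and is zero when rk = 1

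At k = 1 the ratio of ANCOVA to change is (1 - r²)/[2(1 - r)] = (1 + r)/2, that is 0.65/0.75/0.85 for r = 0.3/0.5/0.7.

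**Power.** Noncentral t with noncentrality 0.5k/√[V(1/53 + 1/54)], where V is the variance above, alpha 0.05/m, and N - 2 (change) or N - 3 (ANCOVA) degrees of freedom. For r = 0.5 and k = 1, V is 1 for change and 0.75 for ANCOVA, so the noncentrality is 0.5/√0.0374 = 2.59 against 2.99.

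| Analysed, divisor (k = 1) | Change score, r = 0.3/0.5/0.7 | ANCOVA, r = 0.3/0.5/0.7 |
|---|---|---|
| 53 v 54, m = 1 | 58.1/72.6/91.1% | 76.6/84.1/94.8% |
| 53 v 54, m = 3 | 40.6/56.2/81.6% | 61.0/70.9/88.0% |
| 53 v 54, m = 5 | 33.5/48.8/76.1% | 53.7/64.1/83.8% |
| 43 v 44, m = 1 | 49.5/63.5/84.5% | 67.6/75.9/89.8% |
| 43 v 44, m = 3 | 32.4/46.0/71.4% | 50.3/60.0/79.3% |

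The 43 v 44 rows stand for 18.7% dropout (1 - 87/107), or for the 20 phase 1 focus-group members being counted within the 107.

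Simulation with 10,000 trials per case (53 v 54, k = 1) agrees. At m = 1 it gives 57.8/72.6/91.4% for change and 76.3/84.2/94.8% for ANCOVA. At m = 3 it gives 40.7/56.1/81.3% and 59.7/70.8/87.9%.

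**Price of estimating the slope.** One degree of freedom and a variance inflation of about 1/(N - 4): 1.0% at 107 and 1.2% at 87. The table leaves the inflation out; including it lowers the ANCOVA figures by at most 0.6 point.

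**Equivalent sample size.** 107/[((1 + r)/2)(1 + 1/103)] = 163/141/125 women on the change score to match ANCOVA on 107.

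**Dependence on the SD ratio (53 v 54, m = 3).** With the effect set at 0.5 post-test SD, ANCOVA power does not depend on k.

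| k | Change score, r = 0.3/0.5/0.7 | ANCOVA |
|---|---|---|
| 0.8 | 30.9/43.3/66.8% | 61.0/70.9/88.0% |
| 1 | 40.6/56.2/81.6% | 61.0/70.9/88.0% |
| 1.25 | 49.0/65.1/87.3% | 61.0/70.9/88.0% |

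The gain runs from about 30 points (r = 0.3, k = 0.8) to under 1 point (r = 0.7, k = 1.25, where rk = 0.875).

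**Where ANCOVA can lose.** Take 2:1 allocation, pre-test variance 1, residual variance 0.5, slope 0.4 in the larger arm and 1.3 in the smaller. N × variance is then:

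- Change: 1.5(0.6² + 0.5) + 3(0.3² + 0.5) = 1.29 + 1.77 = 3.06
- Common-slope ANCOVA (pooled slope 0.7): 1.5(0.3² + 0.5) + 3(0.6² + 0.5) = 0.885 + 2.58 = 3.465
- With an arm-by-centred-pre-test term: 1.5(0.5) + 3(0.5) + 0.9² = 3.06

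With the same slopes at 1:1, ANCOVA has 2.81 against 2.90 for change.

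**The case against.** The strongest reply is that nothing planned is wrong. In a randomised two-arm comparison, tests of change are unbiased and valid. That stands; the point is about efficiency only.

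Second, the planned regression of change might already include the pre-test score, and it would then give the same arm p-value as ANCOVA. That is possible, but the covariate is unnamed and the model is only a supplement.

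Third, the size of the gain rests wholly on assumed values. This also stands. The direction is secure for 1:1 allocation or equal slopes; the size is not, which is why ranges are shown.

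Fourth, the ANOVA duplicates the t-test only with two waves. The SAP describes change from pre-test to post-test, but the Protocol has three assessments. If the six-month wave is meant to enter the ANOVA, it is not a duplicate and should not be dropped on that ground.

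Fifth, the Wilcoxon option guards against skewed scores, and the power figures assume normality. That is a reason to keep Wilcoxon as a sensitivity analysis. It is not a reason to leave the deciding test open.

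Finally, the documents do not make Hypothesis 2 primary, and Hypothesis 1 is unaffected. That limits the weight of the point, not its correctness.

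**Conclusion.** The concern holds as an unused gain in precision, not as an error. With equal SDs and r = 0.5, ANCOVA adds about 11 points of power uncorrected and about 15 points with a divisor of 3 or 5, so the Bonferroni correction does not remove the benefit. These figures assume a 0.5 SD effect, 1:1 arms, 107 women analysed and normal scores; other values of r and k move the gain as tabulated, and it is nil at rk = 1. With 1:1 allocation or equal slopes in the two arms, large-sample ANCOVA is not less precise than the change score. If neither condition holds it can be, and the documents state no allocation ratio.

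**What to change.** - For each Hypothesis 2 construct, make the deciding analysis the regression of post-test score on arm plus pre-test score. Equivalently, add the pre-test score to the planned regression of change and promote that model.
- State which assessment is the post-test; one week is the natural reading.
- Apply the promised Bonferroni correction to these p-values, and list the constructs or cite where they are listed. Naming the wave and the constructs is clarification that goes with this change, not a separate error.
- Keep the Wilcoxon test on change as a labelled sensitivity analysis. If the ANOVA has only two waves, drop it as a duplicate of the t-test.
- If allocation is not 1:1, add an arm-by-centred-pre-test term, which in the example above brings ANCOVA level with the change score.

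The cost is SAP wording, with the same data and the same software.
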